### Individual stopping criteria

Individual stopping criteria are described in Table 5.

**Table 5. Individual Toxicity Rules.**

Individual toxicity rules		
Grade	Severity/Seriousness	Action
I	Mild	No action required
II	Moderate	IMP administration may be continued, amended, temporarily suspended or discontinued in accordance with Investigator's clinical judgement and relevant algorithms for the treatment of toxicities
III	Severe, not serious	IMP administration will be discontinued for the subject
	Severe, serious	IMP administration will be discontinued for the subject
IV	Life-threatening	IMP administration will be discontinued for the subject
V	Fatal	Not Applicable

Standard toxicity grading according to the National Cancer Institute Common Terminology Criteria (NCI CTC) for AEs (NCI CTCAE, version 4.0) will be used to grade the AEs for the purpose of applying the toxicity rules. This is owing to the fact that these are the only standardised set of comprehensive criteria available and have proven useful in healthy volunteer and patient Phase 1 studies. Local laboratory normal values will be applied. Abnormal laboratory and other tests and measurements will be repeated whenever feasible and or appropriate, prior to grading in order to ensure consistency and to exclude technical errors. Diurnal variations in laboratory variables and other measurements as well as baseline status and conditions will be taken into account when assessing whether abnormalities constitute a drug related AE and when grading, if applicable.

The CTCAE displays AE/toxicity Grades I through V with detailed clinical descriptions of severity for individual AEs based on a general guideline. The general grade definitions are described as follows:

Grade I: Mild; asymptomatic or mild symptoms; clinical or diagnostic observations only; intervention not indicated.

Grade II: Moderate; minimal, local or non-invasive intervention indicated; limiting age-appropriate instrumental Activities of Daily Living (ADL)\*.

Grade III: Severe or medically significant but not immediately life-threatening; hospitalisation or prolongation of hospitalisation indicated; disabling; limiting self-care ADL\*\*.

Grade IV: Life-threatening consequences; urgent intervention indicated.

Grade V: Death related to AE.

\*Instrumental ADL refer to preparing meals, shopping for groceries or clothes, using the telephone, managing money, etc.

\*\*Self-care ADL refer to bathing, dressing and undressing, feeding self, using the toilet, taking medications, and not bedridden.

The NCI CTCAE criteria and their interpretation are consistent with the standard intensity grading for AEs during clinical studies: Grade I: mild, Grade II: moderate, Grade III: severe

or medically significant but not immediately life-threatening, may constitute Serious Adverse events (SAE)/Suspected Unexpected Serious Adverse Reaction (SUSAR). Grades IV and V constitute SAE/SUSAR.

Non-clinical data as well as potential class effects have identified the risks outlined in sections 6.4.2.1, 6.4.2.3 and 6.4.2.4 (allergic reactions, infusion reactions and anaphylaxis; product specific antibody development).

The grading of the NCI CTCAE criteria related to toxicities and potential AEs (including study related sections on: ‘infusion related reaction’, ‘injection site reaction’, ‘allergic reaction’ ‘anaphylaxis’, ‘Immune system disorders’ – specifically ‘autoimmune disorder’) is considered suitable for this particular IMP, study design and the study populations in conjunction with the CSP specific toxicity and dose progression/escalation rules. No further qualifications are required.

## **8.4 Rationale for Study Design, Doses and Control Groups**

This study is the first time that MOTREM will be given to healthy young subjects.

A standard single dose escalation design is used for this study to evaluate the safety, tolerability and PK of the investigational product in healthy subjects. The study is randomised and double blind (Part B only) to minimise bias and includes placebo to facilitate identification of effects related to administration of drug rather than the study procedures or situation.

For the first two dose levels (Part A) there will be no placebo and only one subject will be dosed, as these dose levels are well below the expected therapeutic dose range and expected to be below the limit of quantification in human blood and therefore not considered informative (9).

### **8.4.1 Justification of Safe Starting Dose**

#### **Regulatory References**

Toxicity studies were performed at INOTREM in accordance with ICH guidance documents S6/R1 and M3 (R2) as well as to EMA’s guidance on repeated dose toxicity (EMEA/CHMP/SWP/488313/2007) and FDA guidance “Immunogenicity Assessment for Therapeutic Protein Products”.

The safe starting dose of LR12 in the first-in-human study MOT-C-104 was estimated according to the principles laid out in the guidance documents “Guidance for Industry: Estimating the Maximum Safe Starting Dose in Initial Clinical Trials for Therapeutics in Adult Healthy Volunteers. FDA/CDER, July 2005” and the “Guideline on Strategies to Identify and Mitigate Risks for First-in Human Clinical Trials with Investigational Medicinal Products CHMP/SWP/28367/07”.

## No Observed Adverse Effect Level (NOAEL) Determination

For establishing the safe starting dose, only the 14-day GLP toxicity study in cynomolgus monkeys with the clinical formulation is considered (MOT-PT-10). In this study, monkeys were exposed to an initial high loading dose for 15 minutes followed by a maintenance dose administered by continuous IV infusion for 14 days. The NOAEL was then set as the highest dose administered in that study (140 mg/kg/day with a loading dose of 20 mg/kg/15 minutes, see Table 6 and Table 7).

### **Human Equivalent Dose (HED) Calculation**

According to the “Guidance for Industry: Estimating the Maximum Safe Starting Dose in Initial Clinical Trials for Therapeutics in Adult Healthy Volunteers. FDA/CDER, July 2005”, normalisation to body surface area is an appropriate method for extrapolating doses between species (hereafter referred to as “HED BS”). However, certain exceptions are made. It is considered that scaling based on body weight (i.e. setting the HED (mg/kg) = NOAEL (mg/kg) and referred to in this document as “HED BW”) may be appropriate for therapeutics that will have little distribution outside the intra-vascular compartment. There is some evidence that LR12 mainly remains in the i.v. compartment after administration. However, distribution of LR12 is not yet fully characterised.

On the other hand, the clearance of LR12 is very fast in monkeys and it is expected to be similar in humans. Since LR12 is planned to be administered continuously by i.v. infusion to maintain steady state concentrations, as it has been done in efficacy pharmacology models, it is necessary to consider exposure time to LR12 at a given plasma concentration/infusion rate in order to determine appropriate safety margins.

For the above mentioned reasons, both approaches HED BS and HED BW will be taken into consideration as well as rate of infusion and time of exposure in order to calculate the safety margin for this FIH study.

#### **8.4.1.1 Determination of Safe Starting Dose**

The safety factor recommended by regulatory guidance documents is 10. However, considering that LR12 is a novel therapeutic agent, we have increased greatly this safety margin.

The first dose planned to be administered to humans is 1 mg as a “loading” dose infused i.v. for 15 minutes. This will be equivalent to a rate of infusion of 0.057 mg/kg/h and to 0.014 mg/kg dose for an individual of 70 kg.

The reference NOAEL and its conversion to HED BS is shown in Table 6. The reference “loading dose” and its conversion to HED BS for the group of animals that have received the highest loading dose in the toxicology study MOT-PT-10 is presented in Table 7.

**Table 6. NOAEL and HED BS.**

Study	Exposure Time 	NOAEL mg/kg/day	NOAEL mg/kg/hour	HED BS  mg/kg/day	HED BS  mg/kg/hour
MOT-PT-10	24 h	140	5.83	45.16	1.88

1: Refers to a period of 24h of a 14-day repeated toxicity study used here as the reference exposure period

2: HED calculated according to FDA Guidance for Industry Estimating the Maximum Safe Starting Dose in Initial Clinical Trials for Therapeutics in Adult Healthy Volunteers (2005) body surface conversion table. Animal dose is divided by a factor of 3.1 for cynomolgus monkeys.

**Table 7. Highest Loading Dose and HED BS.**

Study	Exposure time	NOAEL mg/kg/15 min	NOAEL mg/kg/hour	HED BS  mg/kg/15 min	HED BS  mg/kg/hour
MOT-PT-10	15 min	20	80	6.45	25.81

1: HED calculated according to FDA Guidance for Industry Estimating the Maximum Safe Starting Dose in Initial Clinical Trials for Therapeutics in Adult Healthy Volunteers (2005) body surface conversion table. Animal dose is divided by a factor of 3.1 for cynomolgus monkeys.

According to this, the starting dose rate in mg/kg/h will be 33 times lower than the NOAEL HED BS (1.88 versus 0.057) and 102 times lower than the NOAEL HED BW (5.83 versus 0.057). In terms of total exposure, knowing that the reference taken in toxicology studies is of 24 hours and that total exposure time for human starting dose will be 15 minutes, the total exposure in a one-day period in mg/kg will be 3226 times lower on the basis of HED BS (45.16 versus 0.014) and 10000 times lower on the basis of HED BW (140 versus 0.014).

If the highest loading dose given during the toxicology study is considered, the starting dose rate in mg/kg/h will be 453 times lower by HED BS conversion (25.81 versus 0.057) and a 1403 times lower by HED BW conversion (80 versus 0.057). In terms of total exposure, the total exposure in a 15-minute period in mg/kg will be 461 times lower on the basis of HED BS (6.45 versus 0.014) and 1429 times lower on the basis of HED BW (20 versus 0.014).

These margins are considered to be sufficiently wide to assure safety of healthy volunteers who will receive LR12 for the first time.

### 8.4.1.2 Justification of Dose Escalation Steps

The planned dose escalation scheme of the FIH study MOT-C-104 is summarised in Table 8:

**Table 8. Planned Dose Escalation Scheme.**

Group	Loading dose			Maintenance dose		
	(mg/kg) 15 min	Rate (mg/kg/h)	Total (mg)*	Rate (mg/kg/h)	Total 7h45 (mg/kg)	Total 7h45 (mg)*
1	0.014	0.057	1	-	-	-
2	0.140	0.570	10	-	-	-
3	0.500	2.000	35	0.03	0.23	16.3
4	1.000	4.000	70	0.10	0.78	54.3
5	2.000	8.000	140	0.30	2.33	162.8
6	5.000	20.000	350	1.00	7.75	542.5
7	5.000	20.000	350	3.00	23.25	1,627.5
8	5.000	20.000	350	9.00	69.75	4,882.5

\*Assuming a body weight of 70kg

The second dose planned to be administered to humans is 10 mg as a “loading” dose infused i.v. for 15 minutes. This will be equivalent to a rate of infusion of 0.57 mg/kg/h and to 0.14 mg/kg dose for an individual of 70 kg.

According to this, the second cohort dose rate in mg/kg/h will be 3.3 times lower than the NOAEL HED BS (1.88 versus 0.57) and 10 times lower than the NOAEL HED BW (5.83 versus 0.57). In terms of total exposure, knowing that the reference taken in toxicology studies is of 24 hours and that total exposure time for this cohort will be 15 minutes, the total exposure in a one-day period in mg/kg will be 323 times lower on the basis of HED BS (45.16 versus 0.14) and 1000 times lower on the basis of HED BW (140 versus 0.14).

If the highest loading dose given during the toxicology study is considered, the second cohort dose in mg/kg/h will receive a 45 times lower dose by HED BS conversion (25.81 versus 0.57) and a 140 times lower dose according to HED BW (80 versus 0.57). The total exposure in a 15 minutes period in mg/kg will be 46 times lower on the basis of HED BS (6.45 versus 0.14) and 143 times lower on the basis of HED BW (20 versus 0.14).

From cohorts 3 to 6, the loading dose will be increased incrementally by a factor 2 (or 2.50).

The first maintenance dose rate will be introduced in cohort 3 and is of 16.3 mg at an infusion rate of 0.03 mg/kg/h for a total exposure time of 7h45. This corresponds to 0.23 mg/kg dose for an individual of 70 kg.

According to this, the third dose rate for the maintenance dose in mg/kg/h will be 63 times lower than the NOAEL HED BS (1.88 versus 0.03) and 194 times lower than the NOAEL HED BW (5.83 versus 0.03). In terms of total exposure, knowing that the reference taken in toxicology studies is of 24 hours and that total exposure time for the maintenance dose in humans will be of 7 hours 45, the total exposure in a one day period in mg/kg will be 196 times lower on the basis of HED BS (45.16 versus 0.23) and 609 times lower on the basis of HED BW (140 versus 0.23).

From cohorts 3 to 8, the maintenance dose will be increased incrementally by a factor 3.

For information, in preclinical efficacy pharmacology experiments in LPS-challenged cynomolgus monkeys, LR12 at a loading dose of 10 mg/kg/h for a period of 30 minutes and a maintenance dose of 1 mg/kg/h for 7.5 hours was pharmacologically active. In this model, this dose was able to avoid hypotension and diminish the increase of several pro-inflammatory cytokines by 20-50% in comparison with untreated animals. This dose would approximately correspond to the dose that will be administered to the cohort 5 of the present study if we consider the HED BS and to the dose that will be administered to the cohort 6 if we consider the HED BW. However, an LR12-induced pharmacological effect is not expected in healthy volunteers since their innate immune system would not be activated.

### **Justification of highest dose level**

The anticipated highest dose regimen that will be tested (cohort 8) is a loading dose of 5 mg/kg administered during 15 minutes (20 mg/kg/h) followed by a maintenance dose of 69.75 mg/kg, administered during a period of 7h45 (9 mg/kg/h).

The highest loading dose will be introduced in cohort 6 (Table 3). This dose in mg/kg/h will be 1.3 times lower by HED BS conversion (25.81 versus 20) and 4 times lower if HED BW is used (80 versus 20). For this cohort, the total exposure in a 15 minutes period in mg/kg will be 1.3 times lower on the basis of HED BS (6.45 versus 5) and 4 times lower on the basis of HED BW (20 versus 5).

In a pilot toxicity study (MOT-PT-01), two monkeys received 18.75 mg/kg/h during a period of 24h, meaning 450 mg/kg (Twice higher rate than the maintenance dose planned in cohort 8 if HED BW is considered). In this study no drug-related adverse event was observed. In terms of total dose in a period of one day, cohort 8 individuals will receive 69.75 mg/kg. In comparison to this pilot study, the total dose that will be administered to cohort 8 is around twice lower if HED BS is used (145.2 versus 69.75) and 6 times lower if HED BW is used (450 versus 69.75). In addition, in a GLP cardiovascular function safety pharmacology study (MOT-PT-02), four monkeys received 18.4 mg/kg/h during 24 hours (total dose of 442 mg/kg) and did not show any drug-related adverse event. Therefore, the highest dose is expected to be safe.

Of importance, in order to further minimise the risk to study subjects in study MOT-C-104, the safety of subjects will be monitored closely and escalation to higher dose levels will be allowed only after careful review by the Safety Review Committee of all clinical and laboratory analysis performed in volunteers (see sections 8.2 and 8.3).

#### **8.4.2 Choice of Subjects for Study**

Male subjects, aged between 18 and 45 years considered healthy for their age are planned to be included in Part A (Groups 1 and 2) and B (Groups 3 to 8). The selection criteria are defined such that subjects selected for participation in the study are known to be free from any significant illness which potentially could confound the study results. Healthy subjects are also unlikely to require concomitant treatments which could interfere with the study drug. Female volunteers are not included in this study because investigations on teratogenicity have not been performed.

#### **8.4.3 Route and Rate of Administration**

MOTREM will be administered as an i.v. infusion. In this study, dose levels were calculated from pre-clinical data. Dose escalation will proceed with accordance with Table 1 of adaptive features and will not exceed the mean maximum exposure limits.

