### **8 STUDY DESIGN**

#### **8.1 Overall Study Design and Procedure**

This will be a First in Human (FIH), randomised, placebo-controlled study, with sequential single ascending intravenous dose groups. Single doses of MOTREM (LR12) or matching placebo are planned to be administered following a sequential group design in 26 healthy young male subjects aged from 18 to 45 years.

This study incorporates the use of an adaptive design (8). Study specific adaptive features and their limits are described in Table 1.

Dose escalation and progression will be limited by evaluation of safety and tolerability data governed by toxicity rules (Section [8.3](#)) and will only occur after satisfactory review of all safety and tolerability data by the Safety Review Committee (Section [8.2.3](#)).

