**Table 1. Adaptive Protocol Features.**

Adaptive Study Design Areas	Features	Limits
Dose	
 
1. All anticipated dose levels/dosing regimens in Parts A and B can be adjusted in accordance with PK, safety and tolerability data collected up to the decision making time-point.
 
2. In Part B, the anticipated dosing regimens can be adjusted in accordance with PK, safety and tolerability data collected up to the decision making time-point.
 
3. The term dosing regimen includes (1) the dose level administered as loading dose, (2) the dose level administered as maintenance dose (3) the duration of the loading dose and (4) the duration of the maintenance dose. Accordingly, these can be adjusted individually or in combination.
 
	
 
I. The starting dose for Part A of the study will not exceed 1 mg.
 
II. The maximum dose for Part A will not exceed 10 mg.
 
III. The starting loading dose in Part B will not exceed 0.5mg/kg.
 
IV. The starting maintenance dose in Part B will not exceed 0.03 mg/kg/h.
 
V. The dose increments between the dose levels 1 to 2 in Part A will be no more than 10-fold.
 
VI. The loading dose increments between the dose levels in Part B will be no more than 2.5-fold.
 
VII. The maintenance dose increments between the dose levels in Part B will be no more than 3.5-fold.
 

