Timing	
 
4. Dosing regimens may overlap.
 
5. Cohorts/dosing regimens may be split into sub-groups
 
	
 
I. Protocol specific minimum study progression/escalation requirements for the SRC must be met before dose progression/escalation as described in section 8.2.
 
I. A mandatory sentinel dosing strategy of dosing one subject on IMP on the first day will be used for each cohort. If safety and tolerability is acceptable the remaining subjects of each cohort will be dosed in group sizes of no more than three with a minimum interval of 24 hours between the start of dosing in the first subject on the previous day and the start of dosing on the next day.
 
II. During a dosing day, there will be a minimum interval of 60 minutes between the start of (maintenance) dosing in a subject and the start of dosing in the next subject.
 
III. Additional sentinel or sequential dosing for all cohorts and study parts can be performed at the discretion of sponsor
 

Adaptive Study Design Areas	Features	Limits
Flexible Cohort Sizes	
6. Withdrawn subjects can be replaced at the discretion of the sponsor and investigator, if not withdrawn for safety reasons.
 
7. Replacement subjects may be enrolled in an ongoing cohort, or dosed together as a group or dosed separately.
 
8. The number of subjects in a dose cohort can be extended to gather further information on a dosing regimen.
	and investigator.
Optional Study Parts/Cohorts	9. Optional groups/cohorts may be included to explore additional dose levels and/or dosing regimen.	
I. The maximum extension is 100% of the original group/cohort size at the selected dose level.
 
II. The randomisation will follow the randomisation system of the originally planned dose cohort.
 
III. Study specific toxicity rules (Table 4) apply.

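### Part B has no numerical dose ceiling in the visible text, and one permitted step from 6 mg/kg/h would pass the highest 24 h monkey infusion rate

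*Combined protocol and SAP*

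**What the plan says.** Section 8.1 says where the bounds on adaptation are to be found: "Study specific adaptive features and their limits are described in Table 1". Section 8.4.3 relies on that table and on a further bound: "Dose escalation will proceed with accordance with Table 1 of adaptive features and will not exceed the mean maximum exposure limits".

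The dose limits in Table 1 are numbered I to VII. Part A has a starting dose, a 10-fold step limit and an absolute cap: "The maximum dose for Part A will not exceed 10 mg". Part B has starting doses (0.5 mg/kg load, 0.03 mg/kg/h maintenance) and two step limits: "The loading dose increments between the dose levels in Part B will be no more than 2.5-fold" and "The maintenance dose increments between the dose levels in Part B will be no more than 3.5-fold".

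The planned scheme can be changed. Feature 1 reads: "All anticipated dose levels/dosing regimens in Parts A and B can be adjusted in accordance with PK, safety and tolerability data". Feature 3 counts the durations of both infusions among the adjustable elements. Feature 9 adds: "Optional groups/cohorts may be included to explore additional dose levels and/or dosing regimen". Table 9 reserves two optional Part B cohorts of four subjects, and 8.2.4 sets the data needed to escalate within Part B, optional groups included.

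Section 8.4.1.2 describes the top regimen (5 mg/kg, then 9 mg/kg/h) as the one anticipated. Amendment 4 lowers the cohort 8 maintenance rate to 6 mg/kg/h. It lists only the synopsis and 10.1.1 as affected, so the Table 1 limits stay as they were. Section 6.4.2.2 lists an 8-hour limit on exposure among the measures that reduce risk.

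**The concern.** A fold-step limit bounds the ratio of one dose to the one before it. Without a maximum it does not bound the dose. Part A has a maximum in Table 1, and Part B, where the doses are far larger, has none there. The phrase in 8.4.3 that should supply the bound has no number, so the SRC cannot apply it.

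The subjects are healthy men with no prospect of benefit, and the safety margins in 8.4.1.2 were worked out for the planned regimens only. A regimen above those would meet the written step rule without any stated margin behind it. The same gap affects duration: 6.4.2.2 treats 8 hours as a safeguard, while feature 3 of Table 1 makes duration adjustable and no dose limit restricts it.

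**Working it through.** **Inputs.** Step limits of 2.5-fold (load) and 3.5-fold (maintenance): Table 1, limits VI and VII. Current top maintenance rate, 6 mg/kg/h: Amendment 4. Top load, 5 mg/kg: Table 11. Maintenance duration, 7.75 h. Monkey references: 18.75 mg/kg/h for 24 h (MOT-PT-01) and 18.4 mg/kg/h for 24 h (MOT-PT-02), both in 8.4.1.2; highest load 20 mg/kg over 15 min (Table 7). HED BW equals the monkey dose; HED BS is the monkey dose divided by 3.1 (8.4.1, Table 6).

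**The plan's own figures for 9 mg/kg/h.**
- Monkey total: 18.75 × 24 = 450 mg/kg; by HED BS, 450 / 3.1 = 145.2.
- Human maintenance total: 9 × 7.75 = 69.75 mg/kg.
- Ratios: 145.2 / 69.75 = 2.08; 450 / 69.75 = 6.45; rate by HED BW, 18.75 / 9 = 2.08.

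These agree with the printed margins of about 2, 6 and 2.

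**At the current top rate, 6 mg/kg/h.**
- HED BW: 18.75 / 6 = 3.13.
- HED BS: 18.75 / 3.1 = 6.05, and 6.05 / 6 = 1.01.

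**One permitted maintenance step.** 6 × 3.5 = 21 mg/kg/h.

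| Comparison | Reference | Reference / human dose |
|---|---|---|
| Rate, HED BW, MOT-PT-01 | 18.75 | 18.75 / 21 = 0.89 |
| Rate, HED BW, MOT-PT-02 | 18.4 | 18.4 / 21 = 0.88 |
| Rate, HED BS, MOT-PT-01 | 6.05 | 6.05 / 21 = 0.29 |
| One-day total, HED BW | 450 | 450 / 167.75 = 2.68 |
| One-day total, HED BS | 145.2 | 145.2 / 167.75 = 0.87 |

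The one-day total is 21 × 7.75 + 5 = 167.75 mg/kg. It includes the load, which the printed 69.75 does not. Any step larger than 18.75 / 6 = 3.125-fold passes the MOT-PT-01 rate by HED BW.

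**One permitted loading step.** 5 × 2.5 = 12.5 mg/kg. By HED BS, 6.45 / 12.5 = 0.52; by HED BW, 20 / 12.5 = 1.6.

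**Is 18.75 the highest sustained rate reported?** Section 6.4.2.1 also reports 440 mg/kg/day tolerated for 14 days in a preliminary formulation: 440 / 24 = 18.3 mg/kg/h, slightly lower. The monkey load ran at 80 mg/kg/h, but for 15 minutes only.

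**The case against.** **Table 1 may have lost a limit when the PDF was converted to text.** The row for flexible and optional cohorts is displaced: the limits printed beside feature 9 concern cohort extension, and Amendment 2 cites Limits I to III for feature 8. Amendment 4 cites Limits I and III for features 2 and 3, which fits the visible dose limits poorly, since I is the Part A starting dose and III the Part B starting load. The visible dose limits run I to VII without a gap, but a lost limit cannot be excluded. This stands, and it is why the fix begins with a check of the source.

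**The SRC is not free to choose any dose.** Section 8.2.3 ties its decisions to the protocol, the anticipated doses, the adaptive features and the toxicity rules, and the most cautious option prevails if members disagree. Sentinel dosing and PK data from three active subjects also apply. These are real safeguards. They respond to doses already given, however, and none states a maximum.

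**The rate comparison sets a 7.75 h infusion against a 24 h one.** Section 8.4.1 says that exposure time must be considered. This stands: by HED BW the one-day total keeps a margin of about 2.7.

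**A step up is unlikely.** Amendment 4 went down, calling 6 mg/kg/h sufficient and 9 mg/kg/h not intended for therapeutic use, and optional cohorts need not go higher. This stands as a statement of likelihood. It does not alter what the rule permits.

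**A reader might infer that such a step could be taken without ethics committee approval**, because Amendment 4 was classed as non-substantial for applying the Table 1 features and limits, and 17.3.2 exempts non-substantial amendments. That amendment reduced a dose within a range already justified. The documents do not say how an increase beyond 8.4.1.2 would be classed.

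**Conclusion.** The point holds for the text as it can be read. Part B has no numerical ceiling on dose, rate or exposure, and the bound named in 8.4.3 has no value. One permitted step from 6 mg/kg/h gives 21 mg/kg/h. That is 1.12 times the highest 24 h monkey rate by HED BW (21 / 18.75) and 3.47 times by HED BS (21 / 6.05, using the unrounded 6.048). The one-day total exceeds the monkey total by HED BS only.

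The conclusion assumes that Table 1 is complete as read and that no value for the 8.4.3 limits sits in a document not supplied.

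Three stronger readings are not supported. First, 21 mg/kg/h is not planned. Second, exceeding a dose that monkeys tolerated does not show harm, and the printed margins for the planned regimens are arithmetically correct. Third, a reader might chain successive steps through the optional cohorts to reach much larger doses. With feature 9's own limits unclear in the text, and no statement that those cohorts would escalate, that is too remote to rest a finding on.

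This should be fixed: the gap concerns healthy volunteers in a first-in-human study, and closing it costs little.

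**What to change.** First check Table 1 in the source PDF for a Part B limit missing from the text. If one exists, cite it by number in 8.4.3. If not, add to the Table 1 dose limits, for planned and optional cohorts alike:

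- VIII. Part B loading dose at most 5 mg/kg over 15 min.
- IX. Part B maintenance rate at most 6 mg/kg/h.
- X. Total infusion time at most 8 h.

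State that anything above these needs a substantial amendment with a revised 8.4.1.2. In 8.4.3, replace the undefined exposure term with a reference to limits VIII to X.

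The load cap keeps the printed HED BS margin of 1.3 (6.45 / 5). The rate cap is the Amendment 4 dose. If the sponsor prefers to keep room above it, the cap should in no case exceed the 9 mg/kg/h that 8.4.1.2 justifies, where the rate ratio is 2.08 by HED BW and 6.05 / 9 = 0.67 by HED BS. The time cap repeats 6.4.2.2 and matches 15 min plus 7 h 45 min.

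The cost is three lines in Table 1 and one edit in 8.4.3. No planned group changes, because after Amendment 4 all lie at or below the caps. The SRC loses the freedom to go higher without a substantial amendment.
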